9.2 Atezolizumab Dose Modification

There will be no dose reduction for atezolizumab in this study. Patients may temporarily suspend study treatment for up to 105 days beyond the last dose if they experience an adverse event that requires a dose to be held. If atezolizumab is withheld because of adverse events for more than 105 days beyond the last dose, then the patient will be discontinued from atezolizumab treatment. If a patient must be tapered off steroids used to treat adverse events, atezolizumab may be withheld for additional time beyond 105 days from the last dose until steroids are discontinued or reduced to prednisone dose (or dose equivalent) ≤ 10 mg/day. The acceptable length of interruption will depend on agreement between the investigator and the Medical Monitor. Dose interruptions for reason(s) other than adverse events, such as surgical procedures, may be allowed with Medical Monitor approval. The acceptable length of interruption will depend on agreement between the investigator and the Medical Monitor.

Toxicities associated or possibly associated with atezolizumab treatment should be managed according to standard medical practice. Although most immune-mediated adverse events observed with immunomodulatory agents have been mild and self-limiting, such events should

be recognized early and treated promptly to avoid potential major complications. Discontinuation of atezolizumab may not have an immediate therapeutic effect and, in severe cases, immune-mediated toxicities may require acute management with topical corticosteroids, systemic corticosteroids or other immunosuppressive agents. The investigator should consider the benefit-risk balance a given patient may be experiencing prior to further administration of atezolizumab. Atezolizumab should be permanently discontinued in patients with life-threatening immune-mediated adverse events.

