Patients with unexplained symptoms such as headache, fatigue, myalgias, impotence, constipation, or mental status changes should be investigated for the presence of thyroid, pituitary, or adrenal endocrinopathies. The patient should be referred to an endocrinologist if an endocrinopathy is suspected. Thyroid-stimulating hormone (TSH) and free triiodothyronine and thyroxine levels should be measured to determine whether thyroid abnormalities are present. Pituitary hormone levels and function tests (e.g., TSH, growth hormone, luteinizing hormone, follicle-stimulating hormone, testosterone, prolactin, adrenocorticotrophic hormone [ACTH] levels, and ACTH stimulation test) and magnetic resonance imaging (MRI) of the brain (with detailed pituitary sections) may help to differentiate primary pituitary insufficiency from primary adrenal insufficiency.

Table 4 Management Guidelines for Endocrine Events

Event	Management
Asymptomatic hypothyroidism	
 Continue atezolizumab. Initiate treatment with thyroid replacement hormone. Monitor TSH weekly.
Symptomatic hypothyroidism	
 Withhold atezolizumab. Initiate treatment with thyroid replacement hormone. Monitor TSH weekly. Consider patient referral to endocrinologist. Resume atezolizumab when symptoms are controlled and thyroid function is improving.
Asymptomatic hyperthyroidism	
TSH ≥ 0.1 mU/L and < 0.5 mU/L:
 
 Continue atezolizumab. Monitor TSH every 4 weeks. 
TSH < 0.1 mU/L:
 
 Follow guidelines for symptomatic hyperthyroidism.
Symptomatic hyperthyroidism	
 Withhold atezolizumab. Initiate treatment with anti-thyroid drug such as methimazole or carbimazole as needed. Consider patient referral to endocrinologist. Resume atezolizumab when symptoms are controlled and thyroid function is improving. Permanently discontinue atezolizumab.^c

MRI=magnetic resonance imaging; TSH=thyroid-stimulating hormone.

^a Atezolizumab may be withheld for a longer period of time (i.e., > 12 weeks after event onset) to allow for corticosteroids (if initiated) to be reduced to the equivalent of ≤ 10 mg/day oral prednisone. The acceptable length of the extended period of time must be determined by the investigator.

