^b If corticosteroids have been initiated, they must be tapered over ≥ 1 month to the equivalent of ≤ 10 mg/day oral prednisone before atezolizumab can be resumed.

^c Resumption of atezolizumab may be considered in patients who are deriving benefit and have fully recovered from the immune-related event. Patients can be re-challenged with atezolizumab only after approval has been documented by the investigator (or an appropriate delegate).

Table 4 Management Guidelines for Endocrine Events (cont.)

Event	Management
Symptomatic adrenal insufficiency, Grade 2–4	
 Withhold atezolizumab for up to 12 weeks after event onset.^a Refer patient to endocrinologist. Perform appropriate imaging. Initiate treatment with corticosteroids equivalent to 1–2 mg/kg/day IV methylprednisolone and convert to 1–2 mg/kg/day oral prednisone or equivalent upon improvement. If event resolves to Grade 1 or better and patient is stable on replacement therapy, resume atezolizumab.^b If event does not resolve to Grade 1 or better or patient is not stable on replacement therapy while withholding atezolizumab, permanently discontinue atezolizumab.^c
Hyperglycemia, Grade 1 or 2	
 Continue atezolizumab. Investigate for diabetes. If patient has Type 1 diabetes, treat as a Grade 3 event. If patient does not have Type 1 diabetes, treat as per institutional guidelines. Monitor for glucose control.
Hyperglycemia, Grade 3 or 4	
 Withhold atezolizumab. Initiate treatment with insulin. Monitor for glucose control. Resume atezolizumab when symptoms resolve and glucose levels are stable.

MRI = magnetic resonance imaging; TSH = thyroid-stimulating hormone.

^a Atezolizumab may be withheld for a longer period of time (i.e., > 12 weeks after event onset) to allow for corticosteroids (if initiated) to be reduced to the equivalent of \leq 10 mg/day oral prednisone. The acceptable length of the extended period of time must be determined by the investigator.

^b If corticosteroids have been initiated, they must be tapered over \geq 1 month to the equivalent of \leq 10 mg/day oral prednisone before atezolizumab can be resumed.

^c Resumption of atezolizumab may be considered in patients who are deriving benefit and have fully recovered from the immune-related event. Patients can be re-challenged with atezolizumab only after approval has been documented by the investigator (or an appropriate delegate).

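### Attached endocrine Table 4: the symptomatic hyperthyroidism row says to resume atezolizumab on improvement and then to stop it permanently, with no condition on the stop

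*Combined protocol and SAP*

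**What the plan says.** The table concerned is Table 4 under Endocrine Events in the attached management guidelines, not the severity-grading Table 4 of Section 10.3.2. Its symptomatic hyperthyroidism row has five steps, in this order:

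1. Withhold atezolizumab.
2. "Initiate treatment with anti-thyroid drug such as methimazole or carbimazole as needed".
3. Consider referral to an endocrinologist.
4. "Resume atezolizumab when symptoms are controlled and thyroid function is improving".
5. "Permanently discontinue atezolizumab", carrying footnote c.

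The asymptomatic hyperthyroidism row splits by TSH. From 0.1 to below 0.5 mU/L, atezolizumab continues with TSH checks every 4 weeks. Below 0.1 mU/L the instruction is "Follow guidelines for symptomatic hyperthyroidism".

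Footnote c begins "Resumption of atezolizumab may be considered in patients who are deriving benefit and have fully recovered from the immune-related event" and requires documented approval by the investigator or a delegate before re-challenge.

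In the protocol body, Section 9.2 states: "Atezolizumab should be permanently discontinued in patients with life-threatening immune-mediated adverse events". It also ends atezolizumab after a hold of more than 105 days beyond the last dose, with extra time allowed for a steroid taper.

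**The concern.** Steps 4 and 5 cannot both be followed for the same patient. Step 4 returns an improving patient to treatment. Step 5 ends treatment and does not say for whom. The reader has to supply the missing condition, and different readers may supply different ones.

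The cross-reference widens the reach. A patient with no symptoms and a TSH below 0.1 mU/L meets the same two instructions. The Study Calendar (Section 12) schedules thyroid tests at Cycle 1, Day 1 and every fourth cycle thereafter, so the trial will look for this finding. In the maintenance phase (Section 11.2) atezolizumab is the only study drug, so a permanent stop at that point would end study drug treatment.

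At stake is consistent dosing across a projected 3 centers and 18 patients. The statistical design is not at stake.

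**Working it through.** The plan gives no figure to reproduce and no arithmetic beyond counting applies. The check compares this row with the other attached rows, with footnote c and with Section 9.2.

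**Step 1. Is the pairing normal for these tables?** Count every attached row that contains both a restart and a permanent stop.

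| Attached table | Rows with both | Stop has a condition |
|---|---|---|
| Pulmonary (Grade 2) | 1 | 1 |
| Hepatic (Grade 2) | 1 | 1 |
| Gastrointestinal (Grades 2, 3) | 2 | 2 |
| Endocrine (symptomatic hyperthyroidism; adrenal insufficiency; hypophysitis Grade 2 or 3) | 3 | 2 |
| Ocular (Grade 2) | 1 | 1 |
| Myocarditis (Grade 2) | 1 | 1 |
| Infusion reaction/cytokine release (Grade 2) | 1 | 1 |
| Pancreatic (enzyme elevation Grade 3 or 4; pancreatitis Grade 2 or 3) | 2 | 2 |
| Dermatologic (Grade 3) | 1 | 1 |
| Neuropathy (Grade 2) | 1 | 1 |
| Renal (Grade 2) | 1 | 1 |
| Myositis (Grades 2, 3) | 2 | 2 |
| **Total** | **17** | **16** |

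The exception is symptomatic hyperthyroidism: 17 − 16 = 1. Of the 16 conditioned stops, 15 are tied to failure to resolve to Grade 1 or better, and one (infusion reaction/cytokine release) to no improvement within 24 hours.

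**Step 2. What do the other endocrine rows do?** Five rows of Table 4 say to withhold.

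- Symptomatic hypothyroidism has the identical resume bullet and no stop.
- Hyperglycemia Grade 3 or 4 ends at "Resume atezolizumab when symptoms resolve and glucose levels are stable", with no stop.
- Adrenal insufficiency resumes on resolution and states its stop condition: "If event does not resolve to Grade 1 or better or patient is not stable on replacement therapy while withholding atezolizumab, permanently discontinue atezolizumab".
- Hypophysitis Grade 2 or 3 resumes on resolution, with a stop if the event does not resolve.
- Symptomatic hyperthyroidism resumes and stops without a condition.

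That is 2 with no stop, 2 with a conditioned stop and 1 with an unconditioned stop.

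**Step 3. Does footnote c reconcile steps 4 and 5?** It does not. It governs what may happen after a permanent stop and requires benefit, full recovery and documented approval. Step 4 requires only controlled symptoms and improving function. These are two thresholds for restarting, and neither says when the stop applies.

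**Step 4. Does the missing condition change what happens to a patient?** Three readings of the last bullet are open.

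| Reading of the stop | Symptomatic, improving on treatment | Asymptomatic, TSH stays below 0.1 mU/L |
|---|---|---|
| Applies to everyone in the row | Stop (contradicts step 4) | Stop |
| Applies if the event does not resolve | Resume | Could be stopped, depending on how resolution is defined |
| Applies if life-threatening | Resume | Not stopped by this bullet |

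The readings diverge most for the asymptomatic patient.

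**The case against.** The best case for leaving the row alone is that a sensible investigator would read it as an escalation: hold, treat, restart if better, otherwise stop. Section 9.2 already has a stop rule for life-threatening events, leaves the benefit-risk judgement to the investigator, and refers the reader to the Investigator's Brochure for detail. Footnote c keeps re-challenge open. A wrong reading would err towards stopping the drug, so the cost is lost treatment and not added toxicity. The trigger may also have been lost when the PDF was read.

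Most of this limits the size of the point without removing it. An implied *otherwise* does not say whether the test is non-resolution or a threat to life, and the choice matters for asymptomatic patients. The bullet ends with a full stop and a footnote mark and shows no visible gap, but an extraction loss cannot be excluded without the source.

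Two stronger readings are tempting, and the documents support neither.

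- **That the row orders a permanent stop for a symptom-free laboratory result.** It does not: the last bullet can be followed that way only by ignoring the resume bullet before it. The row is ambiguous; it is not a mandate to stop.
- **That the row is wrong because it conflicts with Section 9.2.** That section does not make life-threatening events the only ground for stopping. Many attached rows stop permanently at Grade 3 (pulmonary, hepatic, ocular and renal events, for example), or at any grade (meningoencephalitis, myasthenia gravis and Guillain-Barré syndrome). Going further than Section 9.2 is common in these tables and does not single out this row.

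Nor is an unconditioned stop unusual in itself. Sixteen other attached rows have one, but none of them also has a resume bullet.

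**Conclusion.** The point holds as a self-contradictory dosing instruction in one row: 1 of the 17 attached rows that contain both a restart and a permanent stop leaves the stop without a condition, and a second patient group is sent to that row. Footnote c does not resolve it.

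The size is small. The documents give no hyperthyroidism rate for this regimen, so the number of the 18 patients affected cannot be estimated and could be zero. No loss of dose is claimed, nor any general conflict with Section 9.2. The PFS6 endpoint, the type I error of 0.10, the 80% power and the rule of at least 6 of 16 are unaffected.

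The conclusion assumes that the bullet in the source PDF reads as it does here. If the source carries a trigger, the point lapses.

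**What to change.** First check the source PDF for a phrase lost after the last bullet. If there is none, add a trigger to that bullet. Two wordings are defensible, and the choice is a clinical one for the sponsor's physicians.

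- **Preferred:** limit the permanent stop to life-threatening immune-mediated hyperthyroidism. This matches a stop rule already in Section 9.2. Asymptomatic patients with TSH below 0.1 mU/L would not meet it, so they would follow only the withhold, treat and resume steps. None of the 16 conditioned stops in the attached tables uses this wording, so it rests on Section 9.2 and not on the tables' own pattern.
- **Alternative:** use a non-resolution condition of the kind in the adrenal insufficiency and hypophysitis rows. The row should then say separately whether it applies to asymptomatic patients, because a persistently low TSH might otherwise count as non-resolution.

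Under either wording, the Section 9.2 rule on holds beyond 105 days continues to apply. The cost is one condition in one bullet at the next amendment, plus one line on asymptomatic patients if the alternative is chosen. Design, sample size and analysis do not change.
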